3.1. General Description

Nigeria is estimated to have the highest incidence of peripartum cardiomyopathy in the world, as high as 1 in 100 deliveries (M. B. Davis, Arany, McNamara, Goland, & Elkayam, 2020). As such, a prospective randomized-controlled study will be conducted at multiple sites in Northern and Southern Nigeria with study participants randomly assigned in a 1:1 fashion to the intervention vs. the control arm over a 12 to 18-month period.

Following informed consent, all participants will have ECGs acquired at baseline and at selected intervals during pregnancy and postpartum (Fig 5 and 6). Half of the participants will be randomized to either undergo:

- AI-ECG screening for cardiomyopathy + baseline echocardiography + AI-ECG age and sex estimation (intervention arm) or
- Standard of care + AI-ECG age and sex estimation only (Zachi I Attia, Paul A Friedman, et al., 2019) (attention control arm).

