7.1. Sample Size Determination

LVEF<50% is not expected to be diagnosed in the control arm due to the lack of routine echocardiograms, but for sample size calculations, we have assumed that 1% will be diagnosed based on literature derived incidence rate of 1 in 100 deliveries (M. B. Davis et al., 2020). With the AI-ECG screening, we hypothesize that an increase in the number of cases will be detected. For sample size estimation consideration, an unpublished, ongoing pilot study conducted in the US estimates the prevalence as 5.3% (3/57) for <=35% and 7% (4/57) for <50%. Sample size estimation is based on a conservative estimate of 4% in the AI-ECG arm. At the alpha=0.05 and 80% power, the sample size is estimated to be 424/group. For the secondary composite endpoint, approximately 5% of the sample is expected to experience hypertensive disorders (Ying, Catov, & Ouyang, 2018). We hypothesize that the addition of AI-ECG will increase the detection of cardiomyopathies and other structural defects of the heart. Accordingly, we assume composite event rates of 5% vs. 10% for the control vs. AI-ECG arm. At 80% power and alpha=0.05, a sample size of 434/group is required. For the final sample size, these estimates are rounded up to 500/group (1000 total) to account for the uncertainties in the calculations. Due to the variability in the occurrence of cardiomyopathy across sites, need to account for study participant withdrawal from the study, no-shows to study visits, and loss to follow up, we plan to enroll 1,400 patients to achieve an accrual target of 1,200 participants while ensuring balanced accrual across all 6 sites.

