7.3. Statistical Hypotheses and planned analyses

7.3.1. Descriptive Statistics

Descriptive statistics including measures of central tendency for numeric variables and frequency distributions for categorical variables will be calculated, as appropriate for all variables. Demographic, clinical, and outcome variables (primary and secondary) will be tabulated for all enrolled study participants. These data will be summarized for the entire cohort and stratified by randomized group and region. We will summarize the measures of diagnostic performance (i.e., AUC, sensitivity, specificity) stratified by study entry to account for the differential follow-up testing that may have occurred as a result of the AI-ECG screening

7.3.2. Primary Hypothesis:

AI-ECG is an effective tool to screen for cardiomyopathy, defined as LVEF < 50%, in pregnant women.

Statistical Hypothesis:

- $H_0: P_{\text{ai-ecg}} = P_{\text{control}}$
- $H_A: P_{\text{ai-ecg}} \neq P_{\text{control}}$

Where P defines the proportion of participants that have documented LVEF <50% by the conclusion of the study.

Primary analysis: A chi-square test without continuity correction will be applied to the resulting two by two table (rows: random treatment assignment, columns LVEF < 50% reported by conclusion of the study). The primary analysis will be conducted at the alpha=0.05 level of significance (two-sided).

7.3.3. Secondary Hypotheses:

AI-ECG will provide consistent performance across race, ethnicity, and postpartum enrollment status.

Secondary analysis: The introduction of stratification factors of race, ethnicity and postpartum status (all unique tables) will be used to produce a stratified contingency table. The Breslow-Day test of homogeneity of the odds ratio will be used to test for effect modification (differential treatment effects by strata). There is the potential for sparse strata with this analysis. If the odds ratio is not estimatable due to zero cells, the empirical logit estimator as well as pooled strata (to increase sample size for each strata) will be utilized.

An AI-ECG is an effective tool to screen for cardiomyopathy at different LVEF cut-off values (<45%, <40%, ≤ 35%).

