Secondary analysis: Within the intervention arm that obtains Echos as a part of the study protocol, the AI-ECG model performance will be evaluated. First, the existing algorithm, without retraining, will be used to evaluate discrimination (area under the receiver operating characteristics curve) at various thresholds for LVEF (i.e., 50% as planned for the primary along with 45%, 40% and 35% as noted here). Performance of the model by the patient stratification factors of Age, Race, Ethnicity, and postpartum status will be considered. For these, the reporting standards outlined in the STARD criteria will be adhered to, e.g., inclusion of measures of precision (confidence intervals) and fractional values associated with measures of performance.

7.3.4. Exploratory Hypotheses:

AI-ECG will improve the diagnosis of cardiovascular disease and associated clinical outcomes among pregnant and postpartum women.

Statistical plan: The analysis of this endpoint will use the same techniques as the primary and secondary analyses. Here, a composite score of any cardiovascular disease diagnoses during the course of the study will be utilized as the outcome measure.

An AI-enhanced point of care screening tool using portable, smartphone-compatible ECG devices (AIPOC-ECG) will be effective for the detection of cardiomyopathies among Black pregnant and postpartum women.

Statistical plan: The primary analysis will utilize the predictions based on the clinical 12 lead ECG machine. This exploratory analysis will compare the model performance on the point of care devices with the clinical standard ECG machine.

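### The secondary composite has no covariate-adjusted comparison, although entry status and baseline blood pressure are available in both arms; the precision given up is small

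*Combined protocol and SAP*

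**What the plan says.** Section 7.1 builds the composite's sample size in two steps. The control rate comes from one component: "For the secondary composite endpoint, approximately 5% of the sample is expected to experience hypertensive disorders". The difference comes from others: "We hypothesize that the addition of AI-ECG will increase the detection of cardiomyopathies and other structural defects of the heart". On that basis, "we assume composite event rates of 5% vs. 10% for the control vs. AI-ECG arm", and "At 80% power and alpha=0.05, a sample size of 434/group is required".

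For the comparison of arms, 7.3.2 gives one test, written for the primary endpoint: "A chi-square test without continuity correction will be applied to the resulting two by two table", two-sided at 0.05. Section 7.3.3 tabulates by race, ethnicity and postpartum status, but only to run a Breslow-Day test of homogeneity. It does not mention the 7.2.2 composite. Section 7.3.4, under the exploratory hypotheses, says "The analysis of this endpoint will use the same techniques as the primary and secondary analyses" and applies this to a composite of cardiovascular diagnoses whose wording differs from 7.2.2. No regression, Mantel-Haenszel or standardised estimate of the arm difference appears.

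Women may enter at any stage of pregnancy or up to 12 months postpartum (3.1, 6.2), and are "randomly assigned in a 1:1 fashion" with no stratification factor named. In both arms, 6.1 schedules blood pressure at baseline. Urine protein (yes/no) is also listed there, but is taken from medical records.

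**The concern.** Entry status should matter for this endpoint. A woman enrolled late postpartum is past the period in which most hypertensive components arise, and 3.3 allows her follow-up to be a single day, against up to 18 months for a first-trimester entrant. Baseline blood pressure is a natural predictor of the same components. The plan recognises that entry matters: 7.3.1 stratifies diagnostic performance by study entry, and 7.3.3 tabulates by postpartum status. It does not use this in the treatment comparison of the composite.

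If these variables predict the hypertensive events, leaving them out makes the interval for the arm difference wider than it need be. A chance difference in the pregnant share between arms then also stays in the estimate. At stake is some efficiency on a secondary endpoint that the plan took the trouble to size.

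**Working it through.** **The plan's own figure.** Inputs from 7.1: 5% vs 10%, 80% power, alpha 0.05, taken as two-sided as in 7.3.2. With pooled variance under the null and no continuity correction:

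n = [1.96·√(2·0.075·0.925) + 0.8416·√(0.05·0.95 + 0.10·0.90)]² / 0.05² = (0.7301 + 0.3121)² / 0.0025 = 434.4

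This is 434 to the nearest whole number, or 435 rounded up, so the stated figure is that of an unadjusted 2x2 test. By the same formula, unadjusted power is 80.0% at 434, 85.2% at 500 and 90.9% at 600 per group. The 600 is the accrual target of 1,200 split 1:1.

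**Share of events that is hypertensive.** If the 5% arises in both arms, hypertensive events are 5 + 5 = 10 of the 5 + 10 = 15 points, or two thirds. The 5-point difference contains none of them.

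**Gain from adjustment.** The documents give no prognostic strengths, so these inputs are assumptions:
- 50-70% pregnant at entry;
- postpartum risk 0.2-0.5 times the pregnant risk;
- 10-20% of women at high baseline risk (raised blood pressure or proteinuria), carrying 3-6 times the risk;
- a constant 5-point increment in every stratum, so that the covariates do not predict the extra detected disease.

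Unadjusted variance (times n per arm) is 0.05·0.95 + 0.10·0.90 = 0.1375. Adjustment removes the between-stratum variance V of the control risk from each arm, so the proportional reduction is 2V/0.1375.

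- *Largest gain* (50% pregnant, ratio 0.2, 15% high-risk at 6 times): the reference risk is 0.05 / [(0.5 + 0.5·0.2)(0.85 + 0.15·6)] = 0.0476. Stratum risks are 0.286, 0.048, 0.057 and 0.010 with weights 0.075, 0.425, 0.075 and 0.425. V = 0.00487; reduction 0.00974/0.1375 = 7.1%.
- *Smallest gain* (70% pregnant, ratio 0.5, 10% high-risk at 3 times): the reference risk is 0.05 / [(0.7 + 0.3·0.5)(0.9 + 0.1·3)] = 0.0490. Stratum risks are 0.147, 0.049, 0.074 and 0.025 with weights 0.07, 0.63, 0.03 and 0.27. V = 0.00085; reduction 0.00170/0.1375 = 1.2%.

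Power = Φ[(0.05·√n − 0.7301)/0.3708], with n divided by (1 − reduction):

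| n per group | Unadjusted | Adjusted, smallest gain | Adjusted, largest gain |
|---|---|---|---|
| 434 | 80.0% | 80.4% | 82.8% |
| 600 | 90.9% | 91.2% | 92.8% |

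At 600 per group the standard error is √(0.1375/600) = 1.51 points. The 95% half-width goes from 2.97 points to between 2.95 and 2.86.

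**Cross-check with a continuous predictor.** Suppose instead that the covariates discriminate the hypertensive events with an assumed AUC of 0.65-0.85, the extra detected disease being unrelated to them. The variance falls by 1.0-8.5%, the required n falls from 435 to between 431 and 399, and power at 600 is 91.2-93.1%. With entry status alone, all hypertensive events in women pregnant at entry, and 50-90% pregnant, the reduction is 3.5% down to 0.4%.

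**Chance imbalance.** With 50% pregnant, the SD of the difference in pregnant share is √(2·0.5·0.5/600) = 2.89 points, and it exceeds 5 points in about 8% of trials; with 70% pregnant, 2.65 points and about 6%. At the strongest contrast (8.3% vs 1.7%), a 5-point imbalance shifts the composite by 0.05·6.7 = 0.33 points, or about 0.2 standard errors.

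**The case against.** The strongest reply is that nothing here is an error. Under randomisation an unadjusted 2x2 test is valid, its sizing reproduces, and 500-600 per group already gives 85-91% power. The prognostic inputs are assumed, and even the favourable case narrows the half-width by only about 0.1 point. All of that stands. It limits the size of the point but does not remove it, because the better estimator needs no new participants.

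A reader might infer more than the documents support:

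- *That the composite is sized mainly on hypertensive disorders.* Only the control rate is. The effect being tested comes from detection of cardiomyopathy and structural disease, which these covariates are not assumed to predict.
- *That the plan prescribes a 2x2 test for the 7.2.2 composite.* This is an inference. Section 7.3.3 assigns it no test, and 7.3.4 covers a differently worded, exploratory composite.
- *That the precision is free.* Urine protein is abstracted from records and may be missing, hypertension history appears only as generic medical history, and 7.4.1 merely reports missing values. Entry status and blood pressure are the dependable covariates.
- *That chance imbalance threatens the result.* A shift of about 0.2 standard errors, in an unlikely draw and at the extreme of the assumptions, is already covered by the ordinary interval.

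One further objection has force. Baseline blood pressure and urine protein partly define the hypertensive components, and 7.2.2 does not say whether a condition already present at entry counts. Until that is settled, adjustment could mean conditioning on events already counted.

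**Conclusion.** The point holds as a modest improvement. No covariate-adjusted estimate of the arm difference is planned for the composite, although entry status and blood pressure are available in both arms and plausibly predict the components behind its control rate. Under the stated assumptions the variance falls by about 1-7%, worth 0.4 to 2.8 percentage points of power at 434 per group and 0.3 to 1.9 at 600. The size rests entirely on those assumptions; the documents support only its direction. Neither the validity of the comparison nor the adequacy of the sample size is in question. Of at least equal practical value is that the 7.2.2 composite would gain an explicitly named analysis.

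**What to change.** In 7.3.3 or 7.3.4, or in the detailed SAP that 7.4.5 promises, pre-specify for the 7.2.2 composite:

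1. A logistic model on arm, pregnant or postpartum at entry, and baseline systolic blood pressure. Add urine protein only with a missing category.
2. The standardised risk difference from that model, with a robust 95% confidence interval, as the main estimate. Keep the uncorrected chi-square as supporting.
3. A rule for missing covariates.
4. A counting rule for women who already meet a hypertensive component at entry, so that the adjustment is for baseline risk and not for events already counted.

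At 600 per group the assumed rates give 30 + 60 = 90 events, enough for a model of this size. Stratifying allocation by entry status is optional and worth considering only if the allocation list can still be changed.

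The cost is some SAP wording, slightly more analysis work and the handling of missing covariates. It needs no extra participants and no new measurements.

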**Figure 5. Patient enrollment flow diagram**

[figure not shown]

Figure 6. Study procedures

All patients will have follow-up and medical record review to ascertain the development of study clinical outcomes. Patients can enter the study at any time point (Fig 6) during pregnancy or the postpartum period (up to 12 months after delivery). All women will have a standard 12-lead ECG performed at the time of enrollment and at pre-specified intervals through 12 months postpartum or study end (whichever is earlier). ECGs will be performed up to 7 times during the study period including during each trimester of pregnancy (up to 3 ECGs), post-delivery ECGs may be taken between delivery and 6 weeks (1 ECG), between 6 weeks and 3 months (1 ECG), between 3 and 5 months (1 ECG), and between 5 and 12 months postpartum (1 ECG). Only participants in the intervention arm will have a baseline echocardiogram as well as simultaneous portable ECGs recorded with near real-time provision of AI-ECG cardiomyopathy prediction. Additionally, a newly positive AI-ECG screen for cardiomyopathy during any of the 6 visits will trigger an echocardiogram for participants in the intervention arm. This strategy for performing echocardiograms was selected as it is not practical to obtain an echocardiogram during each prenatal care visit due to time, skilled expertise required, and cost. In addition, the negative predictive value of the AI-enabled ECG is known to be very high (consistently exceeding 95%) in multiple internal and external patient populations (D. Adedinsewo et al., 2020; Attia et al., 2021; Z. I. Attia et al., 2019). Patients in the intervention group with cardiomyopathy detected on an echocardiogram will have a repeat echocardiogram performed at the end of the study period (or at 12 months postpartum depending on which is earlier) as part of the study protocol to assess for left ventricular recovery (Fig 6).

All echocardiograms will be reviewed by the local cardiologists and performed in accordance with American Society of Echocardiography guidelines for ejection fraction assessment as part of the study. LVEF measurements will be recorded for study participants using REDCap.

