7.2.2. Secondary Study Endpoints

Our secondary endpoints will include:

- A composite outcome of all-cause mortality and adverse cardiovascular events (including cardiomyopathy or systolic heart failure, diastolic heart failure, hypertensive disorders of pregnancy, preeclampsia/eclampsia, valvular heart disease, heart failure-related hospitalization, sustained ventricular arrhythmias, resuscitated cardiac arrest, and other pregnancy-related complications)
- Identification of LVEF $\leq 35\%$, $< 40\%$ and $< 45\%$ at any time among study participants during the study period
- Impact of AI-enabled ECG screening on echocardiography utilization

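### The secondary composite mixes diagnoses that echocardiography can reveal with clinical events, and only one arm has study echocardiograms, so its direction cannot show benefit or harm

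*Combined protocol and SAP*

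**What the plan says.** Section 7.2.2 lists as a secondary endpoint "A composite outcome of all-cause mortality and adverse cardiovascular events". The list includes cardiomyopathy or systolic heart failure, diastolic heart failure and valvular heart disease. It also includes heart-failure hospitalisation, sustained ventricular arrhythmia and resuscitated arrest, then hypertensive disorders, preeclampsia/eclampsia "and other pregnancy-related complications".

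On ascertainment, section 3.1 says: "Only participants in the intervention arm will have a baseline echocardiogram". A newly positive AI-ECG triggers a further echocardiogram, again only in that arm (3.1, 6.1.2). Section 7.1 recognises the consequence for controls: "LVEF<50% is not expected to be diagnosed in the control arm due to the lack of routine echocardiograms".

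On the planned rates, section 7.1 starts from hypertensive disorders ("approximately 5% of the sample is expected to experience hypertensive disorders"), continues "We hypothesize that the addition of AI-ECG will increase the detection of cardiomyopathies and other structural defects of the heart", and concludes that "we assume composite event rates of 5% vs. 10% for the control vs. AI-ECG arm". It derives 434 per group from these rates.

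On use, the statistical methodology row of the Study Summary says the analysis will assess how AI-ECG screening affects maternal outcomes. Section 7.3.4 hypothesises better diagnosis and better related clinical outcomes, and takes any cardiovascular diagnosis during the study as the outcome measure. Exploratory objective 2.3(a) speaks of diagnostic yield.

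**The concern.** The components can move in opposite directions. A diagnosis made by a study echocardiogram is something the strategy is meant to produce. A death, arrest or heart-failure admission is something it is meant to prevent. Pooled into one yes/no outcome, a success of detection and a clinical failure count the same.

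The arms also differ in how hard anyone looks. The intervention arm would show more cardiomyopathy and valvular disease even if true disease were identical in both arms. The composite is planned to be twice as frequent under AI-ECG for that reason.

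What is at stake is the conclusion. A significantly higher composite could be reported as an effect on maternal outcomes, or misread as harm, when it mainly reflects one-sided echocardiography. A real change in clinical events, in either direction, could sit unseen inside it.

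**Working it through.** **Inputs.** Composite rates 5% and 10%, 80% power, alpha 0.05, 434 per group (7.1). Allocation 1:1 (3.1) and accrual target 1,200 (3.2), so 600 per arm. Upper maternal mortality figure 1,074 per 100,000 live births (1.1), used as an *assumed* control death risk, m = 0.01074. Test: two-sided chi-square without continuity correction. Section 7.3.2 states this for the primary endpoint; its use for the composite is assumed.

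**1. The plan's own figure.** With p1 = 0.05, p2 = 0.10 and mean p̄ = 0.075:

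n = [1.96·√(2p̄(1−p̄)) + 0.842·√(p1(1−p1) + p2(1−p2))]² / (p2−p1)²

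= [1.96 × 0.3725 + 0.842 × 0.3708]² / 0.0025 = 434.4.

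This reproduces 434. The same formula for 1% versus 4% gives 424, as stated for the primary endpoint.

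**2. Power for the planned difference.** Power = Φ{[(p2−p1)√n − 1.96·√(2p̄(1−p̄))] / √(p1(1−p1) + p2(1−p2))}.

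At n = 600: (1.2247 − 0.7301)/0.3708 = 1.334, so power is 91%. This is power to find more composite events under AI-ECG.

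**3. Deaths change while the detection gain stays.** Keep the control composite at 5%, with deaths counted inside it. Keep the plan's 5-point detection gain, no overlap between deaths and other components, and equal rates of the components that do not depend on echocardiography.

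- Deaths halved: p2 = 0.10 − 0.01074/2 = 0.0946. At 600 per arm, 30 versus about 57 women. Power to find the composite significantly *higher* under AI-ECG: (1.0932 − 0.7179)/0.3649 = 1.028, so 85% (78% at 500 per arm).
- Deaths doubled: p2 = 0.10 + 0.01074 = 0.1107. (1.4878 − 0.7536)/0.3821 = 1.922, so 97%.
- Every death prevented: p2 = 0.10 − 0.01074 = 0.0893, still 3.9 points above control.

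Halving and doubling deaths give the same sign and, in most trials, the same significant result.

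**4. Range.** The documents give no rate for the clinical events together. With an assumed control rate of 0.5% to 3%, halved, p2 = 0.10 − h/2 runs from 9.75% to 8.5%. Power to find the composite higher is 88% to 68% at 600 per arm.

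**5. When the sign would reverse.** Under these assumptions the expected excess is the detection gain minus the fall in clinical events. With a 5-point gain and a control composite of 5%, clinical events cannot fall by more than 5 points, so the excess cannot turn negative. With a smaller gain it could.

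**The case against.** The plan is fairly open about this. Section 7.1 says the rise comes from detection, objective 2.3(a) calls the aim diagnostic yield, and the 7.3.4 outcome is worded as diagnoses. No section says that a higher composite would be read as benefit or harm, and the Study Summary does not name the composite when it mentions maternal outcomes. Both arms have record review and capture of new clinical diagnoses at visits 2 to 7. Section 7.3.1 tabulates secondary outcomes by arm, and 7.4.5 announces a more detailed SAP.

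Much of this stands. It narrows the fault to the mixed endpoint together with outcome wording that a yield measure cannot support. It does not remove the fault: nothing commits to reporting components or to separating detected diagnoses from clinical events, and record review does not give controls the echocardiograms that reveal these diagnoses.

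A reader might go further in three ways that the documents do not support.

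- *The excess is pure yield.* Hypertensive disorders, preeclampsia/eclampsia and other pregnancy complications do not depend on echocardiography, so an excess mixes detection with true events.
- *The composite rises whatever happens clinically.* That holds only while the detection gain exceeds the clinical change.
- *The secondary sample size is too small, because the 5% rests on hypertensive disorders alone while for the primary calculation "we have assumed that 1% will be diagnosed" in controls.* Section 7.1 does not really expect those control diagnoses, names other structural defects as part of the rise, and rounds up to 500 per group for uncertainty. No shortfall is shown.

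**Conclusion.** The concern holds in this limited form. The expected composite difference is mainly the yield of AI-ECG plus protocol echocardiography. Its direction identifies neither benefit nor harm, so it cannot carry the maternal-outcome wording in the Study Summary or the clinical-outcome part of the 7.3.4 hypothesis.

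The size rests on assumptions. The 1.07% is an upper regional rate per live birth, not a forecast for this trial, where women may enter late postpartum and attend once. The 85% figure also assumes the plan's full 5-point gain, no overlap and the primary endpoint's test. The structural point needs none of these: it follows from the component list and the one-sided echocardiography.

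This is a matter of interpretation of a secondary endpoint. The 434 per group is sound arithmetic, and the primary calculation of 424 per group is untouched. It should be corrected because the change is cheap and alters what the trial can conclude.

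**What to change.** In 7.2.2, or in the SAP announced in 7.4.5, report by arm with 95% confidence intervals:

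- **(A)** Echo-dependent diagnoses: cardiomyopathy/systolic heart failure, diastolic heart failure, valvular heart disease. Label them as diagnostic yield of AI-ECG plus protocol echocardiography.
- **(B)** All-cause death, heart-failure hospitalisation, sustained ventricular arrhythmia and resuscitated arrest, labelled descriptive, with all-cause death also shown alone. Note that classing an admission as heart-failure-related may be influenced by study echocardiogram results, which exist only in the intervention arm and can reach the treating clinicians (6.3).
- **(C)** Hypertensive disorders, preeclampsia/eclampsia and other pregnancy-related complications.

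If the composite is kept, show every component by arm beside it and draw no conclusion about clinical benefit or harm from it. Amend the Study Summary and the 7.3.4 hypothesis so that statements about maternal or clinical outcomes rest on (B) and (C), not on the diagnosis composite.

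The cost is wording and one small table, with no added visits or participants. The case report form is not in the text reviewed, so check that it records each component and whether a diagnosis came from a study echocardiogram. Two limits remain. Group (B) will be imprecise: for death at an assumed 1.07% in both arms, the half-width is 1.96 × √(2 × 0.01074 × 0.98926/600) = 0.0117, about ±1.2 points. Group (A) cannot separate the AI-ECG from the baseline echocardiogram, because every intervention participant has both.
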